8.4 Adverse Events, Serious Adverse Events, and Other Reportable Safety Events

The definitions of an AE or SAE, as well as the method of recording, evaluating, and assessing causality of AE and SAE and the procedures for completing and transmitting AE, SAE, and other reportable safety event reports can be found in Appendix 3.

Adverse events, SAEs, and other reportable safety events will be reported by the participant (or, when appropriate, by a caregiver, surrogate, or the participant's legally authorized representative).

The investigator and any designees are responsible for detecting, documenting, and reporting events that meet the definition of an AE or SAE as well as other reportable safety events. Investigators need to document if an SAE was associated with a medication error, misuse, or abuse.

Investigators remain responsible for following up AEs, SAEs, and other reportable safety events for outcome according to Section 8.4.3. The investigator, who is a qualified physician, will assess events that meet the definition of an AE or SAE as well as other reportable safety events with respect to seriousness, intensity/toxicity, and causality.

8.4.1 Time Period and Frequency for Collecting AE, SAE, and Other Reportable Safety Event Information

All AEs, SAEs, and other reportable safety events that occur after the participant provides documented informed consent, but before intervention randomization, must be reported by the investigator if the participant is receiving placebo run-in or other run-in treatment; if the event causes the participant to be excluded from the study, or is the result of a protocol-specified intervention, including, but not limited to washout or discontinuation of usual therapy, diet, or a procedure.

From the time of intervention randomization through 28 days after cessation of treatment, all AEs, SAEs, and other reportable safety events must be reported by the investigator.

Additionally, any SAE brought to the attention of an investigator at any time outside the period specified in the previous paragraph must be reported immediately to the Sponsor if the event is considered related to study intervention.

Investigators are not obligated to actively seek AEs or SAEs or other reportable safety events in former study participants. However, if the investigator learns of any SAE, including a death, at any time after a participant has been discharged from the study, and the investigator considers the event to be reasonably related to the study intervention or study participation, the investigator must promptly notify the Sponsor.

All initial and follow-up AEs, SAEs, and other reportable safety events will be recorded and reported to the Sponsor or designee within the time frames as indicated in [Table 3](#).

Exception: A positive pregnancy test at the time of initial screening is not a reportable event unless the participant has received study intervention.

Table 3 Reporting Periods and Time Frames for Adverse Events and Other Reportable Safety Events

Type of Event	Reporting Period: Consent to Randomization/ Allocation	Reporting Period: Randomization/ Allocation Through Protocol-specified Follow-up Period	Reporting Period: After the Protocol- specified Follow-up Period	Time Frame to Report Event and Follow-up Information to Sponsor
NSAE	Report if: – due to protocol- specified intervention – causes exclusion – participant is receiving placebo run-in or other run- in treatment	Report all	Not required	Per data entry guidelines

Type of Event	Reporting Period: Consent to Randomization/ Allocation	Reporting Period: Randomization/ Allocation Through Protocol-specified Follow-up Period	Reporting Period: After the Protocol- specified Follow-up Period	Time Frame to Report Event and Follow-up Information to Sponsor
SAE	Report if: – due to protocol- specified intervention – causes exclusion – participant is receiving placebo run-in or other run- in treatment	Report all	Report if: – drug/vaccine related. (Follow ongoing to outcome)	Within 24 hours of learning of event
Pregnancy/Lactation Exposure	Report if: – participant has been exposed to any protocol-specified intervention (eg, procedure, washout, or run-in treatment including placebo run-in) Exception: A positive pregnancy test at the time of initial screening is not a reportable event.	Report all	Previously reported – Follow to completion/ termination; report outcome	Within 24 hours of learning of event
ECI (requiring regulatory reporting)	Report if: – due to intervention – causes exclusion	Report – potential DILI – requiring regulatory reporting	Not required	Within 24 hours of learning of event
ECI (does not require regulatory reporting)	Report if: – due to intervention – causes exclusion	Report – non-DILI ECIs and those not requiring regulatory reporting	Not required	Within 5 calendar days of learning of event
Cancer	Report if: – due to intervention – causes exclusion	Report all	Not required	Within 5 calendar days of learning of event (unless serious)
Overdose	Report if: – receiving placebo run-in or other run- in medication	Report all	Not required	Within 5 calendar days of learning of event
DILI=drug-induced liver injury; ECI=event of clinical interest; NSAE=nonserious adverse event; SAE=serious adverse event.				

8.4.2 Method of Detecting AEs, SAEs, and Other Reportable Safety Events

Care will be taken not to introduce bias when detecting AEs and/or SAEs and other reportable safety events. Open-ended and nonleading verbal questioning of the participant is the preferred method to inquire about AE occurrence.

8.4.3 Follow-up of AE, SAE, and Other Reportable Safety Event Information

After the initial AE/SAE report, the investigator is required to proactively follow each participant at subsequent visits/contacts. All AEs, SAEs, and other reportable safety events, including pregnancy and exposure during breastfeeding, ECIs, cancer, and overdose will be followed until resolution, stabilization, until the event is otherwise explained, or the participant is lost to follow-up (as defined in Section 7.3). In addition, the investigator will make every attempt to follow all nonserious AEs that occur in randomized participants for outcome. Further information on follow-up procedures is given in Appendix 3.

8.4.4 Regulatory Reporting Requirements for SAE

Prompt notification (within 24 hours) by the investigator to the Sponsor of SAE is essential so that legal obligations and ethical responsibilities toward the safety of participants and the safety of a study intervention under clinical investigation are met.

The Sponsor has a legal responsibility to notify both the local regulatory authority and other regulatory agencies about the safety of a study intervention under clinical investigation. The Sponsor will comply with country-specific regulatory requirements and global laws and regulations relating to safety reporting to regulatory authorities, IRB/IECs, and investigators.

Investigator safety reports must be prepared for SUSARs according to local regulatory requirements and Sponsor policy and forwarded to investigators as necessary.

An investigator who receives an investigator safety report describing an SAE or other specific safety information (eg, summary or listing of SAEs) from the Sponsor will file it along with the IB and will notify the IRB/IEC, if appropriate according to local requirements.

8.4.5 Pregnancy and Exposure During Breastfeeding

Although pregnancy and infant exposure during breastfeeding are not considered AEs, any pregnancy or infant exposure during breastfeeding (spontaneously reported to the investigator or their designee) that occurs in a participant during the study are reportable to the Sponsor.

All reported pregnancies must be followed to the completion/termination of the pregnancy.

Any pregnancy complication will be reported as an AE or SAE.

The medical reason (example: maternal health or fetal disease) for an elective termination of a pregnancy will be reported as an AE or SAE. Prenatal testing showing fetus will be born

with severe abnormalities/congenital anomalies that leads to an elective termination of a pregnancy will be reported as an SAE for the fetus.

Pregnancy outcomes of ectopic pregnancy, spontaneous abortion, missed abortion, benign hydatidiform mole, blighted ovum, fetal death, intrauterine death, miscarriage, and stillbirth must be reported as serious events (Important Medical Events). If the pregnancy continues to term, the outcome (health of infant) must also be reported.

8.4.6 Disease-related Events and/or Disease-related Outcomes Not Qualifying as AEs or SAEs

Not applicable

8.4.7 Events of Clinical Interest

Selected serious and nonserious AEs are also known as ECIs and must be reported to the Sponsor.

Events of clinical interest for this study include:

1. Potential DILI events defined as an elevated AST or ALT laboratory value that is greater than or equal to 3× the ULN and an elevated total bilirubin laboratory value that is greater than or equal to 2× the ULN and, at the same time, an alkaline phosphatase laboratory value that is less than 2× the ULN, as determined by way of protocol-specified laboratory testing or unscheduled laboratory testing.*
*Note: These criteria are based on available regulatory guidance documents. The purpose of the criteria is to specify a threshold of abnormal hepatic tests that may require an additional evaluation for an underlying etiology. The study-site guidance for assessment and follow-up of these criteria can be found in the Investigator Study File Binder (or equivalent).
2. AEC >5000 cells/μL at a single time point
3. AEC >1500 cells/μL and confirmed or suspected hypereosinophilic syndrome or eosinophil-associated organ injury; see Appendix 9 for definitions and examples.

8.4.8 Drug-device Combination Products/Combination Medicinal Products – Complaints, PQCs, and Malfunctions

The method of documenting and reporting complaints, PQCs, and malfunctions will occur as below and in Appendix 4. Refer to Appendix 7 for country-specific information and definitions.

To fulfill regulatory reporting obligations worldwide, medical device information associated with AEs will be collected and reported to the Sponsor in the same time frame as AEs per Section 8.4.1 via CRF (paper or electronic) and as per data entry guidelines.

All SAEs due to malfunction will be followed until resolution, stabilization, until the event is otherwise explained, or the participant or associated person is lost to follow-up.

PQCs/malfunctions, including those that involve a participant or any user/associated person, must be reported to the Sponsor. Sponsor shall review reported events by the investigator to fulfill the legal responsibility of notifying appropriate regulatory authorities and other entities about certain safety information relating to the drug-device combination products/combination medicinal products being used in clinical studies.

The investigator is responsible for ensuring that follow-up includes any supplemental investigations as indicated to elucidate the nature and/or causality between the AE and the device constituent of combination product.

8.5 Treatment of Overdose

For purposes of this study, an overdose will be defined as 2 or more doses of study intervention administered <10 days apart.

If an overdose occurs, a CBC with differential to assess absolute eosinophil counts (see Section 6.6.3 and Appendix 9) must be performed prior to the next dose of study intervention. If the overdose is associated with an AE, the participant should have the CBC with differential performed as soon as possible.

8.6 Pharmacokinetics

The decision as to which serum samples collected will be measured for evaluation of PK will be collaboratively determined by the Sponsor. If indicated, these samples may also be assayed and/or pooled for assay in an exploratory manner for additional PD markers. Blood samples collected may be stored and further analysis may be performed, if required.

Samples for PK and ADA should be drawn at the same time prior to study intervention administration.

At Visit 3 (1 day after Randomization) and Visit 8 (1 day after the Week 12 visit), all participants will come to the study site for blood collection (24 hours [\pm 12 hours] after study intervention administration) as outlined in the SoA.

8.6.1 Blood Collection for Serum MK-6194

Sample collection, storage, and shipment instructions for serum samples are provided in the Laboratory Manual.

8.7 Pharmacodynamics

Sample collection, storage, and shipment instructions for pharmacodynamic samples are provided in Laboratory Manual. Blood samples collected may be stored and further analysis may be performed, if required.

8.7.1 Immunogenicity Assessments

Samples for ADA analysis will be collected prior to study intervention administration at the timepoints specified in the SoA. Samples for ADA and PK should be drawn at the same time. Confirmed ADA samples will be assayed for titer. Other assays for neutralizing antibodies, ADA domain mapping and cross-reactivity to WT-IL-2 may be performed. Sample collection, storage, and shipment instructions for serum samples are provided in the Laboratory Manual.

8.7.2 Immunophenotyping

Blood for immunophenotyping will be collected for all participants as outlined in the SoA Section 1.3. Additional samples will be collected from participants that are part of the PK/PD/Biomarker Subpopulation as outlined in Section 1.3.3.

Blood collected for immunophenotyping will be assessed using the Treg - immunophenotyping assay and TBNK assay. For all participants, blood will be collected for use in the TBNK assay. For participants in the Subpopulation, blood will be collected to use in both Treg-immunophenotyping and TBNK assays.

8.8 Biomarkers

The following samples for biomarker research will be collected from participants prior to study intervention administration as specified in the SoA:

- Blood for genetic analysis
- Blood for immunophenotyping
- Blood for PBMC biomarkers
- Blood for serum biomarkers analysis
- Blood for DNA biomarkers analysis
- Blood for RNA biomarkers analysis

Sample collection, storage, and shipment instructions for biomarker samples are provided in the Laboratory Manual.

8.8.1 Planned Genetic Analysis Sample Collection

The planned genetic analysis sample should be drawn for planned analysis of the association between genetic variants in DNA and drug response. This sample will not be collected at the site if there is either a local law or regulation prohibiting collection, or if the IRB/IEC does not approve the collection of the sample for these purposes. If the sample is collected, leftover extracted DNA will be stored for FBR if the participant provides documented informed consent for FBR. If the planned genetic analysis is not approved, but FBR is approved and consent is given, this sample will be collected for the purpose of FBR.

The planned genetic analysis sample should be obtained predose on Day 1, but may be collected at the next scheduled blood draw, if needed. Sample collection, storage, and shipment instructions for planned genetic analysis samples will be in the Laboratory Manual.

8.9 Future Biomedical Research Sample Collection

If the participant provides documented informed consent for FBR, the following specimens will be obtained as part of FBR:

- Leftover samples listed in Section 8.8, except for blood for immunophenotyping

8.10 Visit Requirements

Visit requirements are outlined in Section 1.3. Specific procedure-related details are provided in Section 8.

Scheduling Visits

A visit should occur within the recommended scheduling window shown in the SoA. Study visits that include study intervention dispensation (Section 1.3) should be scheduled at least 10 days apart to avoid overdose (Section 8.5).

Unscheduled Visits are allowed whenever necessary.

Except for Visit 2, all PROs should be completed in the order listed in the SoA before laboratory tests or any other efficacy or safety procedures (Section 8.2.1).

8.10.1 Screening/Rescreening Visits

Screening

Up to 4 weeks before intervention randomization, potential participants will be evaluated to determine whether they fulfill the entry requirements as set forth in Section 5.

Rescreening

Participants are allowed to rescreen once. Participants who are rescreened will retain the original screening number assigned at the initial Screening Visit (Section 8.1.6). Once a participant has started the rescreening process, a new screening period will begin (ie, an additional 4-week window) during which time screening procedures will be repeated. If the participant's original screening laboratory results and procedures were not exclusionary and rescreening is completed within 4 weeks of the initial Screening Visit date, the screening laboratory assessments or procedures do not need to be repeated.

If the informed consent has been updated, participants must be reconsented before rescreening. If no updates have been made, the informed consent from the original screening period should be reviewed with the participant and a verbal reconsent to continue in the study should be documented.

8.10.2 Double-Blind Treatment Period

Each visit should be performed as specified in the SoA.

Participants who satisfy all entry criteria will be randomized (via IRT) to double-blind study intervention at Visit 2 (Day 1). Participants will complete PROs in the order listed in the SoA and specified in Section 8.2.1, before any other procedures are completed, except for Visit 2 (Randomization) where PROs can be completed after confirming eligibility.

Participants will be educated by a trained member of the site staff on appropriate administration of study intervention (Section 8.1.9.3). The first dose of study intervention will be witnessed by a member of the site staff in the clinic *after* completion of all other study procedures (Section 8.1.9.4). Witnessed dosing will occur at visits outlined in the SoA.

CCI

Week 24 Visit

At Visit 10 (Week 24), all procedures for the Double-Blind Treatment Period (Section 1.3.1) need to be completed BEFORE the Week 24 study intervention administration as the Week 24 dosing will be part of the Blinded Extension Period (Section 1.3.2).

8.10.3 Blinded Extension Period

The Blinded Extension Period begins with the participant's Week 24 administration of study intervention. Study procedures are outlined in Section 1.3.2. Participants who were assigned to the placebo group during the Double-Blind Treatment Period will be rerandomized to an active arm as outlined in Section 6.3.1.

Participants who permanently discontinued study intervention will continue to be monitored in the study according to the parameters outlined in Section 8.10.5.

8.10.4 PK/PD/Biomarker Subpopulation Visits

At selected sites, additional PK/PD/Biomarker samples will be collected from participants who consent as outlined in the SoA (Section 1.3.3) in addition to the activities listed in the Double-Blind Treatment and Blinded Extension Periods (Sections 1.3.1 and 1.3.2).

During Visit 2, an additional PK sample will be collected 2 to 10 hours after study intervention administration. Participants will need to remain at, or come back to, the site to have this sample collected. If the PK sample is not able to be collected at Visit 2, then the sample will be collected 2 to 10 hours after study intervention administration at Visit 7.

Participants who discontinue study intervention will no longer be part of this Subpopulation.

8.10.5 Participants Discontinued From Study Intervention but Continuing to be Monitored in the Study

Any participant who prematurely discontinues study intervention will have a Discontinuation Visit as outlined in the SoA (Section 1.3). Participants will be encouraged to continue their participation in the study off study intervention until the end of the study period in which they discontinued, and be followed for all remaining study visits in that period (Section 7.1) as outlined in the SoA with the following exceptions, which are not applicable after study intervention is discontinued.

- Efficacy data, including photographs
- PK, PD, Biomarker sample collection
- Study intervention dispense/return
- Witnessed dose
- Train/retrain participant on self-administration
- Dosing reminder telephone call

Discontinuation Visit assessments should be performed at the time of discontinuation. Any AEs present at the time of discontinuation should be followed in accordance with the safety requirements outlined in Section 8.4.

Concomitant therapies specifically prohibited (see Section 6.5, [\[Table 1\]](#), and Appendix 8) while the participant was on study intervention are no longer prohibited after discontinuation of study intervention, except for live vaccines. See Appendix 7 for country-specific requirements.

Note: At the Discontinuation Visit, IRT will be contacted for closeout purposes.

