9.5 Statistical Methods

9.5.1 Estimand(s)

Estimand for the Primary Efficacy Analysis

The estimand for the primary objective of this study contains 5 attributes:

- Treatment Regimen: MK-6194 or matching placebo
- Target population: Adult Participants with Non-Segmental Vitiligo
- Endpoint: The percent change from baseline in F-VASI at Week 24
- The population-level summary: the difference in the mean percent change from baseline in F-VASI at Week 24 between the treatment group and placebo
- Intercurrent events: Detailed below:

Number	Intercurrent Events	Handling Strategy
Intercurrent Event #1	Discontinuation of MK-6194 or placebo	Treatment Policy Strategy
Intercurrent Event #2	Usage of any medication for the treatment of Vitiligo as listed in Protocol Section 5.2 # 19	Treatment Policy Strategy

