#### **3.5.1 Estimand(s)**

*Estimand for the Primary Efficacy Analysis*

The estimand for the primary objective of this study contains 5 attributes:

- Treatment Regimen: MK-6194 or matching placebo
- Target population: Adult with Non-Segmental Vitiligo
- Endpoint: The percent change from baseline in F-VASI at Week 24
- Population-level summary: the difference in the mean percent change from baseline in F-VASI at Week 24 between the treatment group and placebo

- Intercurrent events: Detailed below:

Number	Intercurrent Events	Handling Strategy
Intercurrent Event #1	Discontinuation of MK-6194 or placebo	Treatment Policy Strategy
Intercurrent Event #2	Usage of any medication for the treatment of Vitiligo as listed in Protocol Section 5.2 # 19	Treatment Policy Strategy

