#### **Primary Efficacy Analysis**

The primary endpoint, the percent change from baseline in F-VASI score at Week 24, will be analyzed using a LDA model for repeated measures. This model will use all available data on F-VASI at baseline and all post-baseline timepoints up to Week 24. In this model, time will be treated as a categorical variable so that no restriction is imposed on the trajectory of the means over time. The analysis model will adjust for treatment, visit, treatment by visit, and baseline vitiligo status (stable, active) and previous JAK inhibitor use (yes, no) based on IRT values. The treatment difference in terms of the mean percent change from baseline at Week 24 will be estimated and tested from this model. Point estimates, 95% CI and p-value for the treatment differences will be provided. An unstructured covariance matrix will be used to model the correlation among repeated measurements. If the unstructured covariance structure fails to converge with the default algorithm, an autoregressive AR(1) or compound symmetric (CS) structure will be used. The LDA method assumes that the mechanism for missing data is MAR. In this study, it is expected that MAR/MCAR mechanisms will underlie most of the missingness, and the proportion of data that are MNAR, driven solely by unobserved values of the study endpoints, will be small. Reasons for discontinuation from the study may include lack of efficacy, AEs, relocation, withdrawal of consent and protocol deviations. Missing data caused by a participant's relocation or data processing issues are likely to be MCAR. Missing data caused by discontinuations due to lack of efficacy may belong to MAR because this type of discontinuation may depend on the observed efficacy outcomes. The MAR or MNAR mechanisms might each underlie the other reasons to some extent. If the assigned study intervention in large part determines the loss of data for these other reasons (such as AEs), the mechanism may be close to MAR since the intervention assignment is an observed variable and included in the analysis model.

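### The primary estimand is treatment policy for stopping study drug, but the protocol collects no F-VASI after the Discontinuation Visit, so the off-treatment Week 24 outcome it needs is not observed

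*Protocol*

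**What the plan says.** **Estimand.** Protocol 9.5.1 and SAP 3.5.1 list two intercurrent events: "Discontinuation of MK-6194 or placebo" and "Usage of any medication for the treatment of Vitiligo as listed in Protocol Section 5.2 # 19". Each is assigned the "Treatment Policy Strategy". The summary measure is "the difference in the mean percent change from baseline in F-VASI at Week 24 between the treatment group and placebo".

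**Data collection.** Under protocol 8.10.5, a participant who stops has a Discontinuation Visit and is encouraged to attend the remaining visits of that study period, "with the following exceptions, which are not applicable after study intervention is discontinued". The first exception listed is "Efficacy data, including photographs". In the Schedule of Activities (1.3.1) the Discontinuation column marks F-VASI and T-VASI, so one assessment is made at the time of stopping. Protocol 7.1 asks for continued follow-up but refers to 1.3 and 8.10.5 for the procedures.

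**Other therapy.** The same section says that prohibited therapies "while the participant was on study intervention are no longer prohibited after discontinuation of study intervention", live vaccines excepted.

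**Analysis.** The LDA uses all available F-VASI up to Week 24 and assumes MAR. SAP 3.5.2 adds: "In this study, it is expected that MAR/MCAR mechanisms will underlie most of the missingness". The first sensitivity analysis is multiple imputation under MAR. The second is a tipping-point analysis that imputes under MAR and then shifts the imputed values.

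**The concern.** A treatment-policy effect at Week 24 averages over everyone randomized and treated, including those who have stopped drug and perhaps started something else. Under 8.10.5 that part of the average is left blank by design, although these participants may be at the visit where it could be measured.

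The SAP's case for MAR concerns why people stop: stopping for lack of efficacy may depend on scores already seen. It does not address what happens after stopping. With no off-treatment scores in the data, the model predicts Week 24 from each participant's own values up to discontinuation and from the course of those who stayed on drug. That is an as-if-treatment-continued quantity. Hypothetical is my word for it, not the documents'.

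The result would thus be reported under one estimand while estimating another. The gap between the two could not be checked afterwards, because the observations that would show it were not made.

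**Working it through.** **Inputs (protocol 9.7 and 9.8, SAP 3.8):** 55 per arm, difference -20 points, SD 33, 15% dropout, overall two-sided alpha 0.0499 (SAP 0.05), Hochberg over two doses sharing one placebo arm.

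**Step 1. Reproduce the stated power of more than 80%.** Evaluable per arm: 55 × 0.85 = 46.75.
- Single comparison at 0.0499: SE = 33 × √(2/46.75) = 6.83, and 20/6.83 = 2.93, giving power of 83.4% (normal approximation).
- Simulated Hochberg, at least one dose significant: 89.2% if both doses have -20, and 75.4% if only one does.

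The stated figure holds for the single comparison and when both doses work.

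**Step 2. How many participants are affected.** If every dropout is a treatment discontinuer: 55 × 0.15 = 8.25 per arm, or 165 × 0.15 = 24.75 overall (about 25).

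**Step 3. Size of the gap.** Let d be the share who stop, and r the fraction of the -20 that remains at Week 24 in active-arm participants who stopped. Placebo participants who stop are taken as unchanged. Neither d as such nor r is given in the documents.

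Treatment-policy effect = -20 × [(1 - d) + d × r]. The MAR analysis targets about -20, so the overstatement is 20 × d × (1 - r).

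With d = 0.15:

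| r | Meaning | Treatment-policy effect | Overstatement |
|---|---|---|---|
| 1 | fully retained | -20.0 | 0 |
| 0.5 | half retained | -18.5 | 1.5 |
| 0 | fully lost | -17.0 | 3.0 (3/17 = 18%) |
| -0.5 | half reversed | -15.5 | 4.5 |

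At r = 0, d = 10% gives -18 (2 points) and d = 20% gives -16 (4 points).

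**Step 4. What the tipping point does.** SAP 3.5.2 shifts imputed active values by c and imputed placebo values by d (the SAP's d, not the share above). With c = 20 on active and no placebo shift, the result is roughly -20 + 0.15 × 20 = -17, the r = 0 case. The grid can pass through that scenario, but the analysis is defined by where significance is lost. It does not single out this or any other point as the treatment-policy estimate.

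**Step 5. Power if the data are collected and the true effect is -17 (SD 33, Hochberg, 0.0499).**
- Both doses at -17: about 84% with 55 per arm, 81% with 51, and 77 to 78% with 47.
- Only one dose at -17, 55 per arm: about 67 to 69%, depending on the SD and on whether rejections in either direction are counted.

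**The case against.** **Efficacy is measured at discontinuation, and the LDA uses it.** True. Collection stops after the Discontinuation Visit, not before it, and the model conditions on each participant's own scores. A visit close to Week 24 might even be assigned to Week 24; the visit-window text is not visible in the public SAP. But a score taken on the day of stopping does not show what follows weeks off drug.

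**The plan already includes all data.** SAP 3.5.2 takes all available F-VASI, and concomitant medication is not among the 8.10.5 exceptions. Both stand, and they make the fix smaller. Neither supplies a score that was never taken.

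**The tipping point covers it.** It probes the assumption, with separate shifts by arm, and it should be kept. It does not estimate the stated estimand.

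**The gap is small and its sign uncertain.** Three points is under half the planned standard error (33 × √(2/47) = 6.8). Therapy started after stopping, in either arm, could widen, narrow or reverse the gap. This stands, and it is why a range is given.

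A reader might also infer that most use of other vitiligo medication will go unobserved. The documents give no rates, and use while still on study drug is followed by F-VASI as scheduled. Only use after stopping is lost.

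**Conclusion.** The concern holds. The strategy in protocol 9.5.1 and SAP 3.5.1 and the collection rule in protocol 8.10.5 contradict each other, and nothing in the visible text reconciles them. Followed as written, the primary analysis would report an as-if-treatment-continued effect under a treatment-policy label.

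On the stated assumptions the overstatement is 0 to 4.5 points, and 3 points (18%) if benefit is fully lost. This rests on reading the 15% dropout as treatment discontinuation, on an on-treatment effect of -20, on unchanged placebo participants, and on an assumed r.

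Three stronger readings are not supported:
- **A known bias of 3 points in favour of MK-6194.** That fixes total loss of benefit, for which the documents give no evidence.
- **A false-positive problem.** In the model above the gap is proportional to the true effect and vanishes when there is none. The issue is what the estimate means and how large it is.
- **That collecting the data preserves power above 80%.** That needs all 55 per arm retained, or nearly so, and both doses effective. Participants who withdraw from the study are not followed (protocol 7.2), and those who stop drug are only encouraged to stay. Power falls below 80% at 47 per arm, or if only one dose works.

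**What to change.** **Preferred.** Amend 8.10.5 so that F-VASI and T-VASI continue, on the existing schedule, at the remaining double-blind visits through Week 24 after study drug is stopped. The primary model needs no change to use these values, and concomitant medication is already recorded. Dosing, stopping rules and permitted therapy are untouched.

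**If that can no longer be done.** Restate the strategy for discontinuation of study drug as hypothetical and align protocol 8.10.5, protocol 9.5.1 and SAP 3.5.1. Before unblinding, prespecify a reference-based supportive analysis (for example jump to reference) alongside the MAR imputation and the tipping point. It also rests on an assumption and does not model newly started therapy, so it supplements those analyses and does not replace them.

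**Cost.** A short skin assessment at visits these participants are already encouraged to attend; a protocol amendment with regulatory and ethics approval in several countries; and possibly a smaller reported effect. Scores for participants already past their visits cannot be recovered.
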